7.2 LOST TO FOLLOW-UP

A participant will be considered lost to follow-up if he or she fails to return at least 2 scheduled study visits and is unable to be contacted by the study site staff after 3 documented attempts.

The following actions must be taken if a participant fails to return to the clinic for a required study visit:

- The site will attempt to contact the participant and reschedule the missed visit, counsel the participant on the importance of maintaining the assigned visit schedule and ascertain if the participant wishes to and/or should continue in the study.
- Before a participant is deemed lost to follow-up, the PI or designee will make every effort to regain contact with the participant (where possible, 3 telephone calls and, if necessary, a certified letter to the participant's last known mailing address or local equivalent methods). These contact attempts should be documented in the participant's medical record or study file.
- Should the participant continue to be unreachable, he or she will be considered to have withdrawn from the study with a primary reason of lost to follow-up.

8 STUDY ASSESSMENTS AND PROCEDURES

8.1 SAFETY AND OTHER ASSESSMENTS

Subjects will come to the clinic for the following protocol-specified visits: Screening, 0H (+2-day window), 6H, 24H, 48H, 7 days (± 1 -day window) and 28 days (± 3 -day window) days post application. It is important that the 6H, 24H and 48H visits be on approximately on time (± 2 -hour window) to ensure engraftment can be properly assessed.

Screening

Once the subject has provided consent to participate, the following required procedures will be completed at the Screening Visit:

- Review of subject eligibility based on inclusion and exclusion criteria
- Vitals: Blood pressure, heart rate and temperature
- Labs:
 - CBC
 - Urine dipstick pregnancy test (females of childbearing potential)
- Screening IGA score and total lesion count
- Screening porphyrin and sebum levels (Pear 3D)
- Screening photographs (Pear 3D)
- Screening pH (pH meter)
- A pre-BPO cheek swab sample will be procured
- Pre- Bioré® sampling facial wash with Cetaphil®
- A pre-BPO Bioré® sample will be obtained

The following procedures will be completed within the Screening Period:

- Subjects will initiate 5-day, at-home pre-treatment with a 5.0% BPO gel daily application to the face (<https://www.perrigo.com/business/product.aspx?ID=88&let=B> Perrigo 5% BP Aqueous Gel) at the same time each day, immediately after the AM Cetaphil® wash. The final BPO gel application should be at least 24 hours prior to study drug application (and therefore likely the morning before the Day 1 (0H) visit)
- Subjects will initiate a 5-day at-home BID Cetaphil® wash at the same time each day, with the PM wash to be held the day before the Day 1 (0H) visit. No other cleansers can be used throughout the study, from the Screening Visit to Day 28/EOS.
- Subjects will complete an in-home patient e-diary during the pre-treatment period

Once the subject's eligibility has been confirmed and pre-treatment BPO period completed, the subject will be enrolled into the study and initiate on-study procedures, including ongoing patient e-diary for Cetaphil® washes.

Treatment Period

Post BPO-period porphyrin level, sebum production, pH, IGA assessment, total lesion count, and photos will be obtained on Day 1, followed by the engraftment assay. Urine dipstick pregnancy test will be obtained for females of childbearing potential. After these measurements are obtained, subjects will wash their face with Cetaphil® (Galderma) in the office and then the single study drug dose will be applied by the PI (OH). The application should take place at least 24 hours after the last morning BPO application. The PI will apply drug once (time point 0H) to the face: cheek/nose (approximately 50 cm²) to Cohort 1 subjects. If there are less than 2 DLTs and no possibly-related SAEs in Cohort 1 during the 7-day safety assessment, the remaining subjects will be enrolled into Cohort 2 to receive single application to the face: cheek/nose. Subjects will then be monitored for at least 30 minutes after the application for any allergic or anaphylactic reactions. Subjects should not wash or shave their face again until the 24H sampling is completed with the exception that the Bioré® strip follicular assessment will be obtained after washing face with Cetaphil® in office. Subjects may then initiate facial cleansing with Cetaphil® wash BID. However, for all office visit days, subjects should hold the morning wash and morning shaving until visit samples have been obtained.

Engraftment sample procurement: Samples for engraftment will be obtained using a Fab-Swab Filtered Air Breathable Sterile Flocked Collection Device (PurFlock® Ultra-Puritan Diagnostics). The face will be quartered into left lateral, left medial, right lateral, right medial for sampling procurement, with mid pupillary line splitting medial and lateral quarters and midline forehead/nose splitting medial quarters. Each sampling will only test a quarter of the face to ensure that sampling post drug application do not remove study drug prior to the next sampling time point and to improve standardization of sampling area. To obtain samples, the swabs should be pressed firmly and rubbed over the designated quadrant for that sample time-point with occasional rotation of the swab for a duration of a minimum of 30 seconds. Please refer to the Laboratory Manual for detailed instructions.

Subjects will be monitored for safety at all study visits: 0H, 6H, 24H, 48H, 7 days and 28 days after the initial application.

Vitals will be taken at study visits: Screening, 24H, 7 days, and 28 days.

The following will be completed at all office study visits (0H, 6H, 24H, 48H, 7 days, and 28 days), unless otherwise specified:

- Assess for any new or existing AEs or SAEs
- Review concomitant medications
- Obtain cheek samples for
 - Porphyrin presence (Pear 3D)
 - Sebum production (Pear 3D)
- Photography (Pear 3D)
- IGA
- Absolute lesion counts
- pH of skin (pH meter)
- Assess engraftment via Fab-Swab Filtered Air Breathable Sterile Flocked Collection Device (PurFlock® Ultra-Puritan Diagnostics) (TaqMan® assay)
- Assess follicular engraftment via Bioré® strip (TaqMan® assay, at 24H only)
- Urine dipstick pregnancy test (females of childbearing potential, at 0H and Day 28 only)

NOTE: Additional vital signs and CBC may be repeated, as clinically indicated.

End of Study (EOS)

Subjects will remain in the study through Day 28, or may discontinue early, as described in protocol section [7.1](#). Subjects will have completed the study upon conclusion of the Day 28/EOS visit procedures. Subjects who discontinue prior to Day 28 should have the EOS visit scheduled as soon as possible, in

order to complete final safety assessments, prior to discontinuation from the study.

Early Discontinuation of Subjects

Subjects may voluntarily withdraw from the study at any time. A subject's participation in the study may be terminated if it is deemed by the PI or Sponsor that it is unsafe for the subject to continue in the study. Subjects who discontinue prior to completing the DLT evaluation period (i.e., prior to completion of Day 7 procedures) for reasons other than a DLT, will be replaced.

Notification of early subject discontinuation from the study and the reason for discontinuation will be made to Sponsor and will be clearly documented on the appropriate eCRF.

Study Termination

The study may be stopped at his/her study site at any time by the site PI. Sponsor may stop the study (and/or the study site) for any reason with appropriate notification. Both the Sponsor and the PI reserve the right to terminate the study at any time. Should this be necessary, both parties will arrange discontinuation procedures and notify the appropriate regulatory authority(ies), and IRBs. In terminating the study, Naked Biome and the PI will assure that adequate consideration is given to the protection of the subjects' interests.

Adverse Events (AEs)

AEs occurring during the study will be recorded on an AE CRF. If AEs occur, the first concern will be the safety of the study participants.

Prior/Concomitant Therapies and Medications

At screening, all therapies and medication taken up to 2 months prior to the Screening Visit should be recorded on the eCRF. At each study visit, any therapies or medications taken by the subject since the last visit will be captured.

8.2 ADVERSE EVENTS (AEs) AND SERIOUS ADVERSE EVENTS (SAEs)

8.2.1 DEFINITION OF ADVERSE EVENT (AE) AND SERIOUS ADVERSE EVENTS (SAE)

ADVERSE EVENTS (AEs)

An AE is any untoward medical occurrence in a subject or clinical investigation subject administered a pharmaceutical product and that does not necessarily have a causal relationship with this treatment. An AE can therefore be any unfavorable and unintended sign (including an abnormal laboratory finding), symptom, or disease temporally associated with the use of a medicinal (investigational) product, whether or not related to the medicinal (investigational) product. In addition, during the screening period, AEs will be assessed regardless of the administration of a pharmaceutical product.

NOTE: AEs must be collected once informed e-consent has been obtained, regardless of whether or not the subject has been administered study drug.

AEs will be assessed, documented, and recorded on the AE form throughout the study (i.e., after informed e-consent has been obtained). At each visit, the PI will begin by querying for AEs by asking each subject a general, non-directed question such as "How have you been feeling since the last visit?" Directed questioning and examination will then be done as appropriate. All reported AEs will be documented on the appropriate CRF/eCRF.

SERIOUS ADVERSE EVENT (SAEs)

An SAE is defined as an event that meets at least 1 of the following criteria:

- Is fatal or life-threatening.
- Requires inpatient hospitalization or prolongation of existing hospitalization, unless hospitalization is a result of:
 - A routine treatment or monitoring of the studied indication not associated with any deterioration in condition.

- An elective or preplanned treatment for a pre-existing condition that is unrelated to the indication under study and has not worsened since signing the ICF.
- A treatment on an emergency outpatient basis for an event not fulfilling any of the definitions of a SAE and not resulting in hospital admission.
- Any social reasons and respite care, in the absence of any deterioration in the subject's general condition.
- Results in persistent or significant disability, incapacity, or a substantial disruption of a person's ability to conduct normal life functions.
- Constitutes a congenital anomaly or birth defect.
- Is considered to be an important medical event or a medically significant event that may not result in death, be immediately life-threatening, or require hospitalization but may be considered serious when, based upon appropriate medical judgment, the event may jeopardize the subject or may require medical or surgical intervention to prevent 1 of the outcomes listed above.

All cancer AEs are SAEs. In addition, the Sponsor considers any abortion (spontaneous or nonspontaneous) as an SAE.

Pre-planned surgeries or procedures for pre-existing, known medical conditions for which a subject requires hospitalization is not reportable as an SAE.

Any pre-planned surgery or procedure should be clearly documented in the site source documents by the medically qualified PI at the time of the subject's entry into the study. If it has not been documented at the time of the subject's entry into the study, then it should be documented as an SAE and reported to Sponsor.

To ensure subject safety, every SAE, regardless of suspected causality (including events that may not be associated with the study drug[s] but may be associated with a study procedure or disease progression), unless otherwise specified by the Protocol, occurring after the subject has signed the e-ICF and up to the last study visit, whichever is later, must be reported to the Sponsor (or designee) within 24 hours of learning of its occurrence. Any SAEs occurring more than 30 days after the last dose of study drug should be reported to the Sponsor, or its designee, only if the PI suspects a causal relationship to the study drug. An SAE occurring at a different time interval or otherwise considered completely unrelated to a previously reported SAE should be reported separately as a new event. Previously planned (i.e., before providing informed e-consent) surgeries should not be reported as SAEs unless the underlying medical condition worsens over the course of the study.

Information about all SAEs is collected and recorded on the Adverse Event Report Form in the eCRF. The PI must assess and record the causal relationship of each SAE to each specific study drug.

The PI must also complete the Serious Adverse Event Report Form, in English, notify the Sponsor and, if necessary, send the completed and signed form to the Sponsor or designee within 24 hours of becoming aware of the SAE. The PI must provide a causality assessment, that is, assess whether there is at least a reasonable possibility that the SAE is related to the study treatment: suspected (yes) or not suspected (no).

Investigational site personnel must report any new information regarding the SAE within 24 hours of becoming aware of the information in the same manner that the initial SAE Report Form was sent. Follow-up information is recorded on an amended or new SAE Report Form, with an indication that it is follow-up to the previously reported SAE and the date of the original report. The follow-up report should include information that was not provided on the previous SAE Report Form, such as the outcome of the event (e.g., resolved or ongoing), treatment provided, action taken with study drug because of the SAE (e.g., dose reduced, interrupted, or discontinued), or subject disposition (e.g., continued or withdrew from study participation). Each recurrence, complication, or progression of the original event should be reported as follow-up to that event, regardless of when it occurs.

The treating PI will determine AEs by:

- Active query for any systemic symptoms
- Limited facial physical examination
- Utilization of Investigator Assessment of Tolerability Scale (0 = None; 1 = Slight; 2 = Moderate; 3 = Intense) for assessment of:
 - Skin Dryness
 - Skin Peeling
 - Irritant/Allergic Contact Dermatitis
 - Hyperpigmentation
 - Skin Erythema
 - Conjunctival Injection
 - Ocular Irritation
 - Mucosal Toxicity
- Assessment of disease status using IGA Score and Acne Lesion Count

Toxicities that warrant subject discontinuation from the trial, as deemed appropriate by the PI, include but are not limited to: ulceration, extreme redness, worsening of acne, extreme skin irritation, extreme ocular irritation, extreme mucosal irritation, extreme contact dermatitis.

REPORTING

AEs that begin or worsen after informed e-consent was obtained should be recorded on the Adverse Event Report Form in the eCRF. Conditions that were already present at the time of informed e-consent should be recorded on the Medical History form in the eCRF. AEs (including laboratory abnormalities that constitute AEs) should be described using a diagnosis whenever possible rather than by individual underlying signs and symptoms. When a clear diagnosis cannot be identified, each sign or symptom should be reported as a separate AE.

The term "disease progression" should be recorded as an AE/SAE itself only if there are no other identifiable AEs/SAEs associated with the disease progression at the time of reporting. For events associated with disease progression, the relevant signs and symptoms should be reported using a diagnosis whenever possible, rather than the individual underlying signs and symptoms. When a clear diagnosis cannot be identified, each sign or symptom should be reported as a separate AE. If the events resulting from disease progression meet the criteria for an SAE (e.g., resulted in hospitalization, a life-threatening event, or death), the specific event(s) should be reported as an SAE(s). In both cases (i.e., AEs or SAEs related to disease progression), for each event it should be indicated whether the event (diagnosis or signs and symptoms) is related to disease progression.

The occurrence of AEs should be sought by nondirective questioning of the subject during the screening process after signing the ICF and at each visit during the study. AEs may also be detected when they are volunteered by the subject during the screening process or between visits, or through physical examination, laboratory test, or other assessments. To the extent possible, each AE should be evaluated to determine:

- The severity.
- Whether there is at least a reasonable possibility that the AE is related to the study treatment: suspected (yes) or not suspected (no).
- The start and end dates, unless unresolved at final follow-up.
- The action taken regarding study drug.
- The event outcome (e.g., not recovered/not resolved, recovered/resolved, recovering/resolving, recovered/resolved with sequelae, fatal, unknown).
- The seriousness, as per SAE definition provided.

Unlike routine safety assessments, SAEs are monitored continuously and have special reporting requirements.

All AEs should be treated appropriately. If an AE is treated with a concomitant medication or non-drug therapy, this action should be recorded on Adverse Event Report Form in the eCRF and the treatment should be specified on the Prior/Concomitant Medications or Procedures and Non-Drug Therapy form in the CRF/eCRF.

Once an AE is detected, it should be followed until it has resolved or until it is judged to be permanent; assessment should be made at each visit (or more frequently if necessary) of any changes in severity, the suspected relationship to the study drug, the interventions required to treat the event, and the outcome.

LABORATORY TEST RESULTS

Laboratory abnormalities that constitute an AE in their own right (considered clinically meaningful, induce clinical signs or symptoms, require concomitant therapy, or require changes in study drug) should be recorded on the Adverse Event Report Form in the CRF/eCRF. Whenever possible, a diagnosis rather than a symptom should be provided (e.g., "anemia" instead of "low hemoglobin"). Laboratory abnormalities that meet the criteria for AEs should be followed until they have returned to normal or an adequate explanation of the abnormality is found. When an abnormal laboratory test result corresponds to a sign or symptom of a previously reported AE, it is not necessary to separately record the laboratory test result as an additional event.

Laboratory abnormalities that do not meet the definition of an AE should not be reported as AEs. Severity does not automatically indicate an SAE unless it meets the definition of serious, as defined, and/or per the PI's discretion.

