There is no *in vivo* data to date on the safety or clinical efficacy of a topical live *P. acnes* microbiome transplant. As described in our Pre-IND meeting, there are no well substantiated animal models for inflammatory acne and we are working with human-specific bacteria. Therefore *in vivo* animal clinical and toxicology studies will not yield clinically relevant results that would be applicable for human use. Sponsor rationale, in accordance with FDA correspondence, is that animal clinical and toxicology studies are not relevant or useful when we are using human-specific bacteria absent well-substantiated animal models for inflammatory acne for pre-human efficacy testing (Mirshahpanah and Maibach 2007). The best, most relevant, and only useful model to test our lead drug candidate is first in humans (Mirshahpanah P, Howard Maibach 2007), (Achermann et al. 2014). Additional literature on previous human studies for probiotics and acne are listed in the following references (Baquerizo et al. 2014), (Wei et al. 2016), (Thiboutot et al. 2009).

Outside of known association of *P. acnes* with acne vulgaris, below is an accrued list of rare opportunistic infections associated with *P. acnes*. *P. acnes* has been observed in other infections such as implant-associated infections, soft tissue, periodontal, periocular, cardiovascular system, deep-organ tissues infections, and may also have a role in relation to pulmonary infection as the bacteria can be isolated from lungs and lymph nodes. Routes of infection is often from the subject own commensal flora (normal skin or oral tract) (Whitman et al. 2012), (Kwon and Suh 2016). The expanded multi-locus sequence typing scheme based on 7 housekeeping genes and 2 putative virulence genes developed by McDowell et al gives a good resolution and revealed CC types which seem to have an increased capacity to cause infections and others that are rarer or found mainly among healthy individuals. (McDowell et al. 2012), (McDowell et al. 2013).

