Strain HP4G1 contains the deoR repressor gene, and thus may not be associated with acne. Further, the strain has a PAp60/PAmce allele combination found in non-invasive *P. acnes* strains and lacks 2 of 4 genes involved in iron uptake, which is of importance for growth in the human body at conditions with low iron access. Notably, regarding CAMP factors 1-4, which are expected to be involved in pathogenicity and are involved in co-hemolysin with *Staphylococcus aureus* (*S. aureus*), HP4G1 had a mutation in the CAMP 2 gene leading to an extension of the gene as the stop codon was interrupted. This variant has not been observed before and as CAMP factor 2 is described as having properties for co-hemolysin and exotoxin, this may lower the pathogenic potential of the strain. Moreover, the strains belong to the CC72 clonal complex which, compared to CC5, contains strains less commonly isolated from healthy humans or individuals with infections. HP4G1 was found to be a ST100-like type not previously reported and most likely has a non-functional CAMP2 gene due to a mutation in the stop

codon. Therefore, HP4G1 is most likely less virulent than *P. acnes* in general with a low risk of causing infections.

Porphyrin is a known inflammatory metabolite involved in the pathogenesis of acne. Porphyrin is produced by the *P.acnes* bacterium and is a photosensitizing agent. Dermatologists routinely use blue and red light therapies to selectively target *P.acnes*-produced coproporphyrin III and protoporphyrin IX, respectively, thereby eliminating *P.acnes* and improving disease. As stated above, HP4G1 has a repressor of porphyrin production, called *deoR*. *In vivo*, the HP4G1 strain produces less porphyrin than acne-associated strains that lack the *deoR* repressor operon. Despite that the HP4G1 strain is a low porphyrin producer, the fact that it is applied in significant quantities (10^5 CFU/cm²) and (10^6 CFU/cm²), could lead to a temporary increase in porphyrin upon application. This hypothetical increase could be photosensitizing to subjects, as such, photosensitivity has been included as a theoretical side effect of HP4G1 application.

We are addressing the risk of these opportunistic infections through the selection of genotypic and phenotypic characteristics most associated with health and with the implementation of appropriate exclusion criteria to eliminate subjects that may have increased risk of a *P. acnes* infection.

Exclusion Criteria addressing above

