Subjects who screen fail may be considered for enrollment at a later date, but must re-sign the ICF and repeat screening procedures, if any screening procedures will be performed outside of the Screening period from the time of the first informed e-consent.

Replacement of Subjects

If a subject is discontinued from the study for any reason other than a dose-limiting toxicity (DLT) prior to completion of the DLT assessment window, a replacement subject will be enrolled at the same dose level as the discontinued subject. To be evaluable for the DLT observation, a subject must receive a dose of NB01 and either completes all safety procedures through Day 7 or experiences a DLT prior to Day 7. It is possible over-enrollment of subjects may occur in order to have 10 safety-evaluable subjects.

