7 STUDY INTERVENTION DISCONTINUATION AND PARTICIPANT DISCONTINUATION/WITHDRAWAL

7.1 PARTICIPANT DISCONTINUATION/WITHDRAWAL FROM THE STUDY

Participants are free to withdraw from participation in the study at any time.

Participants will remain in the study through Day 28, or may discontinue early if any of the following criteria are met:

- PI decision
- Subject withdrawal of consent
- Subject is lost to follow-up
- Unacceptable Toxicity (exacerbation of IGA 1 point higher than baseline)
- Sponsor termination of the trial

A PI may discontinue a participant from the study for the following reasons:

- Pregnancy
- Failure to comply with the study procedures, including inability to receive study drug or missing study appointments
- If any clinical AE, laboratory abnormality, or other medical condition or situation occurs such that continued participation in the study would not be in the best interest of the participant
- Disease progression, which requires discontinuation of the study intervention

The reason for participant discontinuation from the study will be recorded on the Case Report Form (CRF)/electronic CRF (eCRF).

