8.2.2 DEFINITION OF DOSE-LIMITING TOXICITIES (DLTs)

Dose-limiting toxicities (DLTs) are defined as AEs occurring during the first 7 days after NB01 application that are not due to the subject's underlying disease, are not clearly attributable to other etiologies, and meet any of the following toxicity criteria:

Dermatologic Toxicities:

- Skin Dryness Score of 3
- Skin Peeling Score of 3
- Irritant/Allergic Contact Score of 3
- Hyperpigmentation Score of 3
- Skin Erythema Score of 3
- Exacerbation of disease determined by an increase in IGA score 1 point beyond baseline screening score

Ocular Toxicities:

- Conjunctival injection score of 3
- Eye irritation score of 3

Mucosal Toxicities:

- Mucosal Irritation Score of 3

If any systemic toxicities develop, the Sponsor will pause the study for further review before proceeding. If 2 or more subjects experience a DLT, or in the event of an SAE that is at least possibly-related to study treatment, the Sponsor will pause the study to discuss with the PI and regulatory authorities, if needed.

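### Ulceration is named as a reason to withdraw a subject but is not a dose-limiting toxicity, so a non-serious local ulcer can fall outside the two-DLT limit

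*Combined protocol and SAP*

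**What the plan says.** **Withdrawal.** Section 8.2.1 gives an open list of toxicities that justify taking a subject off study at the PI's discretion: "Toxicities that warrant subject discontinuation from the trial, as deemed appropriate by the PI, include but are not limited to: ulceration". Six more follow: extreme redness, worsening acne, and extreme skin irritation, ocular irritation, mucosal irritation and contact dermatitis. Section 7.1 has its own toxicity criterion, defined only by the acne grade: "Unacceptable Toxicity (exacerbation of IGA 1 point higher than baseline". It also lets the PI withdraw a subject for any clinical AE.

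**DLT definition.** Under Section 8.2.2 an AE is a DLT if it occurs in the first 7 days, is not due to the underlying disease or clearly due to something else, "and meet any of the following toxicity criteria". The criteria are a score of 3 on one of eight tolerability items, or a one-point IGA rise over screening. There is no item for other severe events or for events leading to withdrawal.

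**Evaluability and replacement.** Section 5.5 says that when someone leaves early "for any reason other than a dose-limiting toxicity (DLT) prior to completion of the DLT assessment window, a replacement subject will be enrolled". The newcomer receives the leaver's dose. To be evaluable, a dosed subject "either completes all safety procedures through Day 7 or experiences a DLT prior to Day 7". Section 8.1 repeats the replacement rule.

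**Escalation and pause.** Fewer than two DLTs in Cohort 1 is the condition for moving on (Sections 4.1, 6.1.1 and 8.1). Section 8.1 adds that there must be no possibly related SAE. Two DLTs, or one at least possibly related SAE, pause the study (Section 8.2.2), and so does systemic toxicity: "If any systemic toxicities develop, the Sponsor will pause the study for further review before proceeding". Sections 4.1 and 11.1.6 leave the opening of Cohort 2 to a meeting of the PI and the Medical Monitor.

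**The concern.** The withdrawal list and the DLT list do not agree. The sponsor regards ulceration as bad enough to justify ending a subject's participation, yet gives it no place in the count that governs escalation. The replacement rule adds to this. A subject withdrawn early for an uncounted event is not evaluable, so both the event and the subject leave the two-in-five calculation and a new subject takes the slot.

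This is a first-in-human study of a live organism, the next dose is ten times higher (10^6 against 10^5 CFU/cm²), and each cohort has only five evaluable subjects. At stake are the DLT-triggered pause and the accuracy of the DLT count as a summary of what happened in a cohort.

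**Working it through.** The plan states no operating characteristic for its escalation rule (Section 10.2 gives no sample-size or power estimate), so there is no figure to reproduce. The check is a comparison of the two lists, two worked cases and an illustration under assumed rates.

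**Step 1. The two lists side by side**

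| Withdrawal toxicity (8.2.1) | Nearest DLT item (8.2.2) |
|---|---|
| Ulceration | none |
| Extreme redness | erythema score 3 |
| Worsening acne | IGA rise of 1 |
| Extreme skin irritation | irritant/allergic contact score 3 |
| Extreme ocular irritation | eye irritation score 3 |
| Extreme mucosal irritation | mucosal irritation score 3 |
| Extreme contact dermatitis | irritant/allergic contact score 3 |

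Six of the seven match, at least broadly. Ulceration does not, and the toxicity criterion in Section 7.1 does not cover it.

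**Step 2. Two cases.** Suppose two of the first five Cohort 1 subjects develop local, non-serious, drug-attributed ulcers needing treatment, with no score of 3 and no IGA rise. No other DLTs occur.

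- *Both are withdrawn on Day 3.* As written, neither is evaluable and both are replaced: 5 + 2 = 7 dosed, 0 DLTs in 5 evaluable, no DLT-triggered pause. If the ulcers counted: 2 DLTs in 5, limit reached, pause.
- *Both stay to Day 7.* As written: 5 dosed, no replacements, still 0 DLTs in 5. If the ulcers counted: 2 in 5.

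**Step 3. Effect on the count.** Let q be the per-subject chance of such an ulcer by Day 7. It is an assumption, as the documents give no rate. With no listed DLTs, the count stays below 2 with certainty as written, by construction. If the ulcers counted:

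P(fewer than 2 in 5) = (1 − q)^5 + 5q(1 − q)^4

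If every such subject is withdrawn and replaced, the expected number dosed to reach five evaluable is 5/(1 − q).

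| q | (1 − q)^5 | 5q(1 − q)^4 | Below limit, if counted | Below limit, as written | Difference (points) | Expected dosed, as written |
|---|---|---|---|---|---|---|
| 1% | 0.9510 | 0.0480 | 99.9% | 100% | 0.1 | 5.05 |
| 2% | 0.9039 | 0.0922 | 99.6% | 100% | 0.4 | 5.10 |
| 5% | 0.7738 | 0.2036 | 97.7% | 100% | 2.3 | 5.26 |
| 10% | 0.5905 | 0.3281 | 91.9% | 100% | 8.1 | 5.56 |
| 20% | 0.3277 | 0.4096 | 73.7% | 100% | 26.3 | 6.25 |

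**Step 4. If listed DLTs also occur.** Let p be the rate of listed DLTs, also assumed, and treat the two kinds of event as mutually exclusive. As written, with every ulcer withdrawn and replaced, the DLT rate among evaluable subjects is p/(1 − q). If ulcers counted, it is p + q. Each rate goes into the formula of Step 3. At p = 10%:

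- q = 5%: 0.10/0.95 = 0.105 gives 91.1%; 0.15 gives 83.5%; difference 7.6 points.
- q = 10%: 0.10/0.90 = 0.111 gives 90.2%; 0.20 gives 73.7%; difference 16.4 points before rounding.
- q = 20%: 0.10/0.80 = 0.125 gives 87.9%; 0.30 gives 52.8%; difference 35.1 points.

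At q = 1% and 2% the same formulas give differences of 1.4 and 2.8 points (91.7% against 90.3%, and 91.6% against 88.8%). An uncounted ulcer thus matters more when other DLTs are already using up the allowance.

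**The case against.** **Other rules catch the worse cases.** The DLT count is not the only limit before the higher dose. Section 8.1 also requires zero possibly related SAEs, and Section 8.2.2 pauses the study for a single one. An ulcer may be classed as serious on medical judgement (Section 8.2.1), and one of the definitions of possible relatedness in Section 8.3 can be met by timing alone. An ulcer bad enough for withdrawal might also be scored 3 for erythema or contact dermatitis, since the scale has one-word anchors. All this stands, and it confines the point to non-serious local ulcers without a listed score of 3. None of it makes those ulcers count.

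**The limit does not decide escalation.** A reader might infer that two uncounted ulcers would send the trial to the higher dose. The documents do not support that. Sections 6.1.1 and 8.1 are worded as if Cohort 2 follows from the count, but Sections 4.1 and 11.1.6 place a decision by the PI and Medical Monitor in between. The sponsor is notified of each early discontinuation and its reason (Section 8.1). The percentages above describe the DLT count, not the escalation decision.

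**Withdrawal changes little after a single application.** No further dosing is avoided, AEs are followed to resolution, and early leavers have an end-of-study visit. So it would be wrong to infer that safety data are lost. What is lost is the place of the event and the subject in the two-in-five rule.

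**Infection.** A reader might extend the point to application-site infection with equal force. Section 2.2 does say that the species "has been observed in other infections such as implant-associated infections, soft tissue, periodontal, periocular", and no DLT item covers infection. But Section 8.2.1 does not name it, Section 2.2 calls such infections rare and considers the risk low for this strain, and the sponsor's answer is prevention: "We are addressing the risk of these opportunistic infections through the selection of genotypic and phenotypic characteristics most associated with health", together with exclusion criteria. Every subject also has at least 10 inflammatory lesions in the application area (Section 5.1), so an unqualified infection item would be hard to tell from acne.

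**A bare ulceration item would be too sensitive.** Every existing criterion has a threshold. Without one, a trivial erosion would weigh as much as an intense reaction. This is right, and the fix includes a threshold.

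**Conclusion.** The mismatch is real for ulceration and follows from the text alone. A local, non-serious, drug-attributed ulcer in the first 7 days, with no listed score of 3 and no IGA rise, is outside the DLT count. If it leads to withdrawal before Day 7 is completed, the subject is outside the five evaluable subjects as well.

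The size depends wholly on an event rate that the documents do not give. With no listed DLTs, the effect on the count is negligible at 1–2% per subject and about 2, 8 and 26 points at 5%, 10% and 20%. It is larger if listed DLTs also occur. Nothing in the documents indicates that the higher rates are likely. The calculations assume independent subjects with a common rate. The expected numbers dosed, and the comparison with listed DLTs present, also assume that every affected subject is withdrawn and replaced.

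This is a cheap improvement to a safety rule. It does not show that oversight fails or that either dose is unsafe.

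**What to change.** Add one item to the DLT list in Section 8.2.2: *application-site ulceration that leads to discontinuation or requires treatment, within 7 days of application and not clearly attributable to another etiology*. The lead-in to that section already imposes the last two conditions, so they may be left implicit.

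Optionally, add a second item with the same kind of threshold: *application-site infection, clinically distinct from acne, that requires antimicrobial treatment or leads to discontinuation*.

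Sections 5.5 and 8.1 then work as worded: a subject withdrawn for a listed event has had a DLT, is evaluable and is not replaced. Other withdrawals at the PI's discretion can stay as they are, so that worsening acne remains under the IGA criterion.

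The cost is one or two lines of text. No new visit, form or assessment is needed, because Section 8.2.1 already provides for AE questioning and a limited facial examination. The downside is a possibly less favourable DLT count, including an occasional false DLT where an ulcer has another cause that cannot be clearly shown.
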